Study Plan of

**A RANDOMIZED, CONTROLLED, DOUBLE-BLIND,
MULTICENTER CLINICAL TRIAL ON HOME PARENTERAL
NUTRITION USING AN OMEGA-3 FATTY ACID ENRICHED
MCT/LCT LIPID EMULSION**

The HOME Study

(HPN WITH OMEGA-3)

STUDY IDENTIFICATION NO.: HC-G-H-1403

NCT03282955

Date of final applicable study plan: 21.05.2021

Marketing Authorization Holder:

**B. Braun Melsungen AG
Germany**

Organized and Financed by:

**B. Braun Melsungen AG
Division Hospital Care
[name]
[name]
Germany**

STUDY OVERVIEW

Title of Study	A randomized, controlled, double-blind, multicenter clinical trial on home parenteral nutrition using an Omega-3 fatty acid enriched MCT/LCT lipid emulsion – The HOME Study (HPN with OMEGA-3)
Investigational Products	
Investigational test product:
 
Lipidem® / Lipoplus® 200 mg/ml (in the following referred as Lipidem)
 
Investigational reference product:
 
Lipofundin® MCT/LCT / Medialipide® 20% (in the following referred as Lipofundin MCT)

Phase	IV
Study Design	Prospective, randomized, controlled, double-blind, multicenter clinical trial performed in two parallel groups
Number of Sites & Countries	Up to 15 sites, planned countries: Poland, Belgium, France, Italy, Netherlands, Spain and United Kingdom
Sample Size	160 patients in total (80 per group)
Indication	Supply of energy, including a readily utilizable lipid component (medium-chain triglycerides) and essential omega-6 fatty acids and omega-3 fatty acids, as part of parenteral nutrition when oral or enteral nutrition is impossible, insufficient or contraindicated.
Primary Objective	Proof of safety and tolerability of home parenteral nutrition (HPN) with an Omega-3 fatty acid enriched MCT/LCT lipid emulsion in adult patients with chronic intestinal failure (CIF) in need of long-term HPN
Primary Variable	The primary endpoint of the study is the change of liver function parameters defined as the sum of the N(0,1)-transformed differences in bilirubin, Alanine transaminase (ALT) and Aspartate transaminase (AST) from baseline to visit 2.
Secondary Objectives	Further safety and efficacy evaluation
Secondary Variables	
Variables indicated with * are calculated values
 
Safety
 
 • Hepatic function 
 ▪ Bilirubin (total and conjugated) ▪ Alanine transaminase (ALT) ▪ Aspartate transaminase (AST) ▪ AST/ALT ratio* ▪ Alkaline phosphatase (ALP) ▪ Gamma-glutamyl transpeptidase (GGT) • Blood count and coagulation 
 ▪ White blood cells (WBCs)

- Red blood cells (RBCs)
- Hemoglobin (Hb)
- Hematocrit (Hct)
- Platelets
- International normalized ratio (INR) (if not possible prothrombin time [PT = Quick-value] is accepted)
- Activated partial thromboplastin time (aPTT)

- Other biochemical parameters
 - Blood glucose
 - Electrolytes (Na, Cl, K, Ca, Mg, P)
 - Serum creatinine
 - Triglycerides
 - Cholesterol
 - High-density lipoprotein (HDL) cholesterol
 - Low-density lipoprotein (LDL) cholesterol
 - C-reactive protein (CRP)
 - α -Tocopherol/Vitamin E (facultative if routinely assessed)

 - Triene:tetraene ratio* obtained from fatty acid pattern in plasma

- Adverse events (AEs)

Efficacy

- Fatty acid pattern in plasma and RBCs
- BMI*

Other variables

- Demographic data
 - Age
 - Gender
 - Ethnic origin
 - Body height
 - Body weight

- Anamnesis
 - Medical history relevant with regard to HPN
 - Pathological classification of IF

	
 ○ Underlying disease ▪ Concomitant disease(s) ▪ Ongoing medications ▪ Lipid emulsion(s) during the last 6 months ▪ Anamnestic peculiarities 
 • Physical examination • Vital signs • Body weight change* • Quality of life (EQ-5DTM) • Concomitant medication • Energy requirements • PN regimen prescription • Treatment compliance* • Intake of oily fish meals • Study termination
Patient Inclusion / Exclusion Criteria	
Inclusion criteria
 
 1. Signed informed consent available 2. Male or female patients ≥ 18 years of age 3. Patients with chronic intestinal failure receiving HPN including lipids in whom the parenteral macronutrients have not been changed by more than 10% for at least 3 months 4. Patients receiving ≥ 3.0 g lipids/kg body weight per week 
Exclusion criteria
 
 1. Persistent high total bilirubin values in medical history of last 6 months ($> 40 \mu\text{mol/l}$) 2. Patients in whom PN was interrupted for longer than 4 continuous weeks in the preceding 6 months 3. Patients with history of cancer and anti-cancer treatment within the last 2 years 4. Hypersensitivity to egg, fish, peanut or soya-bean protein or to any of the active substances or excipients 5. Patients treated in the past or currently with Teduglutide 6. Contraindications to investigational products (if available from medical records) including: 
 • Severe hyperlipidemia, including severe hypertriglyceridaemia (≥ 1000 mg/dl or 11.4 mmol/l)

	
 • Severe coagulopathy • Intrahepatic cholestasis • Severe hepatic insufficiency • Severe renal insufficiency in absence of renal replacement therapy • Acute thromboembolic events • Fat embolism • Aggravating haemorrhagic diatheses • Metabolic acidosis 
7. General contraindications to parenteral nutrition (if available from medical records) including:
 
 • Unstable circulatory status with vital threat (states of collapse and shock) • Acute phase of cardiac infarction or stroke • Unstable metabolic conditions (e.g. decompensated diabetes mellitus, severe sepsis, coma of unknown origin) • Inadequate cellular oxygen supply • Disturbances of the electrolyte and fluid balance (e.g. hypokalaemia and hypotonic dehydration) • Acute pulmonary edema • Decompensated cardiac insufficiency 
8. Positive test for HIV, Hepatitis B or C (from medical history)
 
9. Known or suspected drug or alcohol abuse
 
10. Patients who are unwilling or mentally and/or physically unable to adhere to study procedures
 
11. Participation in another interventional clinical trial in parallel or within three months prior to the start of this clinical trial
 
12. Any medical condition that in the opinion of the investigator might put the subject at risk or interfere with patients participation
 
For women with childbearing potential (i.e. females who are not chemically or surgically sterile or females who are not post-menopausal)
 
13. Women of childbearing potential tested positive on standard pregnancy test (urine dipstick)
 
14. Lactation
 
15. Women of childbearing potential who do not agree to apply adequate contraception
 
16. Persons of legal age who are the subject of a legal protection measure or who are unable to express their consent
				
Investigational Test Product	
Lipidem
 
1000 ml emulsion contain:
 
 
 Medium-chain triglycerides	100.0 g	
 
 Long-chain triglycerides (soybean oil)	80.0 g	
 
	Medium-chain triglycerides	100.0 g	Long-chain triglycerides (soybean oil)	80.0 g
Medium-chain triglycerides	100.0 g				
Long-chain triglycerides (soybean oil)	80.0 g				

	
Omega-3 fatty acid triglycerides 20.0 g
 
Essential fatty acids
 
 
 Linoleic acid (Omega-6)	38.4 – 46.4 g	
 
 Alpha-Linolenic acid (Omega-3)	4.0 – 8.8 g	
 
 Eicosapentanoic acid (EPA) and		
 
 Docosahexanoic acid (DHA)	8.6 – 17.2 g	
 
 
Additional excipients are: all-rac-α-Tocopherol, egg lecithin, glycerol, ascorbyl palmitate, water for injections
 
Excipient(s) with known effect
 
 
 Sodium (as sodium hydroxide and sodium oleate)	2.6 mmol/l	
 
 
 
 Energy content	7990 kJ \approx 1910 kcal	
 
 Theoretical osmolality	approx. 410 mOsm/kg	
 
 NaOH or HCl for titration to pH 7.4	< 0,5 mmol/l	
 
 pH	6.5 – 8.5	
 
	Linoleic acid (Omega-6)	38.4 – 46.4 g	Alpha-Linolenic acid (Omega-3)	4.0 – 8.8 g	Eicosapentanoic acid (EPA) and		Docosahexanoic acid (DHA)	8.6 – 17.2 g	Sodium (as sodium hydroxide and sodium oleate)	2.6 mmol/l	Energy content	7990 kJ \approx 1910 kcal	Theoretical osmolality	approx. 410 mOsm/kg	NaOH or HCl for titration to pH 7.4	< 0,5 mmol/l	pH	6.5 – 8.5
Linoleic acid (Omega-6)	38.4 – 46.4 g																		
Alpha-Linolenic acid (Omega-3)	4.0 – 8.8 g																		
Eicosapentanoic acid (EPA) and																			
Docosahexanoic acid (DHA)	8.6 – 17.2 g																		
Sodium (as sodium hydroxide and sodium oleate)	2.6 mmol/l																		
Energy content	7990 kJ \approx 1910 kcal																		
Theoretical osmolality	approx. 410 mOsm/kg																		
NaOH or HCl for titration to pH 7.4	< 0,5 mmol/l																		
pH	6.5 – 8.5																		
Investigational Reference Product	
Lipofundin MCT
 
1000 ml emulsion contain:
 
 
 Medium-chain triglycerides	100 g	
 
 Long-chain triglycerides (soybean oil)	100 g	
 
 
Essential fatty acids
 
 
 Linoleic acid (Omega-6)	48.0 – 58.0 g	
 
 Alpha-Linolenic acid (Omega-3)	5.0 – 11.0 g	
 
 
Additional excipients are: all-rac-α-Tocopherol, egg lecithin, glycerol, sodium oleate, water for injections
 
 
 Energy content	8095 kJ \approx 1935 kcal	
 
 Theoretical osmolarity	approx. 380 mOsm/l	
 
 NaOH or HCl for titration to pH 7.4	< 0,5 mmol/l	
 
 pH	6.5 – 8.5	
 
	Medium-chain triglycerides	100 g	Long-chain triglycerides (soybean oil)	100 g	Linoleic acid (Omega-6)	48.0 – 58.0 g	Alpha-Linolenic acid (Omega-3)	5.0 – 11.0 g	Energy content	8095 kJ \approx 1935 kcal	Theoretical osmolarity	approx. 380 mOsm/l	NaOH or HCl for titration to pH 7.4	< 0,5 mmol/l	pH	6.5 – 8.5		
Medium-chain triglycerides	100 g																		
Long-chain triglycerides (soybean oil)	100 g																		
Linoleic acid (Omega-6)	48.0 – 58.0 g																		
Alpha-Linolenic acid (Omega-3)	5.0 – 11.0 g																		
Energy content	8095 kJ \approx 1935 kcal																		
Theoretical osmolarity	approx. 380 mOsm/l																		
NaOH or HCl for titration to pH 7.4	< 0,5 mmol/l																		
pH	6.5 – 8.5																		
Investigational Products Administration	
Method of Administration
 
The administration of the investigational products (IPs) is performed intravenously.
 
Dosage
 
IP will be delivered as the lipid part of the parenteral nutrition (PN). Besides the lipid PN contains glucose, amino acids, electrolytes, trace
																		

	
elements and vitamins and will be administered according to the individual patient's normal prescription. The weekly dose of IP will be at least 3.0 g lipid per kg body weight (BW) (corresponding 15 ml emulsion per kg BW and week).
 
Treatment Duration
 
Treatment with IP is projected for a period of 8 weeks on average and will not end before Visit 2.

Visit Schedule	
Screening
 
 ▪ Preferably during a regular patient monitoring visit ▪ Patient information and signature of informed consent form (patient information sheet might be provided to the patient prior the visit) ▪ Verification of inclusion and exclusion criteria ▪ Pregnancy test (urine dipstick), if applicable 
Randomization
 
 ▪ After check of all inclusion and exclusion criteria the patient will be randomized. 
Baseline
 
The baseline assessment is performed after randomization on the day of screening.
 
Documentation of:
 
 ▪ Demographic data ▪ Anamnesis ▪ Physical examination 
Assessment of safety, efficacy and other variables (blood samples will be taken the earliest 3 hours after the last PN infusion):
 
 ▪ Vital signs ▪ Laboratory values from routine blood samples 
 • Hepatic function (incl. blood samples for central laboratory analyses of primary variable) • Blood count and coagulation • Other biochemical parameters ▪ Blood samples for central laboratory analyses of fatty acid pattern in RBCs and plasma ▪ QoL ▪ Concomitant medication ▪ AEs continuously from start of study 
The patient will be provided with a patient diary for documentation of IP

	
administration on a daily base. At baseline visit the patient diary will be handed out for the treatment period until visit 1.
 
Prescription of PN including IP:
 
 ▪ Treatment with IP will start within one week after baseline visit ▪ If applicable, changes in prescription will be documented continuously throughout the course of the study 
Visit 1 = 4 weeks after start of IP infusion
 
Study visit 1 should be preferably the same day of week and day time as the baseline visit. If this is not possible, it should be the same interval between PN infusion and visit day as it was for baseline (e.g. if baseline visit was after a day free of PN, visit 1 should be after a day free of PN as well).
 
Assessments and procedures:
 
 ▪ Pregnancy test (if applicable) 
Assessment of safety, efficacy and other variables (blood samples will be taken the earliest 3 hours after the last PN infusion):
 
 ▪ Vital signs ▪ Body weight ▪ Laboratory results 
 • Hepatic function (incl. blood samples for central laboratory analyses of primary variable) • Blood count and coagulation • Other blood biochemistry parameters ▪ Treatment compliance will be documented in the electronic case report form (eCRF) on the basis of patient diary entries ▪ Concomitant medication ▪ AEs 
The investigator will collect the first part of the patient diary and check for accurateness and completeness. The data will be enter into the eCRF.
 
A new patient diary will be handed out for the treatment period until visit 2.
 
Visit 2 (final visit) = 4 weeks after visit 1
 
Study visit 2 should be preferably the same day of week and day time as the baseline visit (and/or visit 1). If this is not possible, it should be the same interval between PN infusion and visit day as it was for baseline (e.g. if visit 1 was after a day free of PN, visit 2 should be after a day free of PN as well).
 
Assessment and procedures:
 
 ▪ Pregnancy test (if applicable) 
Assessment of safety, efficacy and other variables (blood samples will be taken the earliest 3 hours after the last PN infusion):
 
 ▪ Vital signs
--	--

	
 ▪ Body weight ▪ Laboratory results 
 • Hepatic function (incl. blood samples for central laboratory analyses of primary variable) • Blood count and coagulation • Other blood biochemistry parameters ▪ Blood samples for central laboratory analyses of fatty acid pattern in RBCs and plasma ▪ QoL ▪ Treatment compliance will be documented in the eCRF on the basis of patient diary entries ▪ Concomitant medication ▪ AEs 
Patient diary will be collected and data entered in the eCRF
 
Visit 2 is the final study visit for the patient and study termination page of the eCRF will be completed.
 
After this final visit no IP must be administered. The PN treatment will continue according to the decision of the physician with a regularly used lipid emulsion.

Duration of Study per Patient	
Start of study: with randomization
 
Treatment period (infusion of IP):
 
 ▪ Start of IP infusion within one week after randomization ▪ Treatment with IP is projected for a period of 8 weeks on average and will not end before visit 2 
End of study: Final visit (study visit 2)

Study Schedule	
Planned start: Q1 / 2018
 
Planned recruitment time: 5.5 years
 
Planned last patient out: Q2 / 2023

Statistical Methods	
Two sample t-test for mean difference assuming equal variances (testing non-inferiority)
 
Descriptive statistics including methods for the comparison of two groups (t-test, U test, χ^2 test)

Randomization / Blinding	
Patients will be assigned at a 1:1 ratio to receive either Lipidem or Lipofundin MCT. The allocation to one of the two treatment groups will be performed by permuted block randomization with stratification for study site.
 
The study is double-blind.

Data and Safety Monitoring Board (DSMB)	
A DSMB will not be appointed.

Statistical Analysis and Evaluation

Statistical methods

All programming of tables, figures, listings and statistical analyses will be performed using SAS® version 9.4 (or higher). The planned statistics will be performed in accordance with the principles outlined by the guideline ICH E9.

The primary endpoint of the study is the change of liver function parameters defined as the sum of the N(0,1)-transformed differences from baseline in ALT, AST, and bilirubin after 8 weeks of treatment. It is the aim to demonstrate non-inferiority of the primary endpoint with respect to 'deterioration in liver function' using the non-inferiority margin $\delta=1.151$. This margin was derived as ' $\sigma/2$ ' from a previous study on the use of lipid emulsions in HPN patients which provided a standard deviation of 2.3029 for the specified endpoint. The non-inferiority will be shown using the two-sample t-tests for mean differences assuming equal variances under the following conditions:

- distribution : normal
- method : exact
- number of sides: 1
- alpha : 0.025
- mean difference : 1.151 (= non-inferiority margin δ).

The primary analysis will be performed for the Valid case set (FAS for sensitivity). No imputation will be performed.

Thus, the t-test will compare the (one-sided) null hypothesis

- $H_0: \Delta_T \geq \Delta_S + \delta$

against the alternative hypothesis

- $H_1: \Delta_T < \Delta_S + \delta$

on the level of 0.025, where Δ_T and Δ_S represent the increase of the primary endpoint upon T=test and S=standard. Non-inferiority (with non-inferiority margin $\delta=1.151$) can be concluded, if the VCAS analysis yields an upper limit of the two-sided 95% confidence interval (or one-sided 97.5% confidence interval) for the treatment contrast of the primary endpoint lower than 1.151 and if this result is confirmed by the corresponding FAS analysis.

Superiority of T vs S, i.e. $H_0: \Delta_T \geq \Delta_S$ vs. $H_1: \Delta_T < \Delta_S$, is demonstrated simultaneously, if the upper limit of the confidence interval is below zero for both the FAS analysis and the VCAS analysis.

Given the non-inferiority of T vs. S, the following procedure will be performed subsequently:

- breakdown of the multiple primary endpoint to its components ALT, AST, and bilirubin with unchanged level (Lehmacher *et al.*, 1991).

Further methods are descriptive statistics including standard procedures for the comparison of two groups (t-test, U test, χ^2 test).

Interim Analysis

No interim analyses are planned.

Level of significance and power

The primary endpoint will be tested one-sided with an significance level of $\alpha=0.025$.

Tests of secondary variables will be carried out in the area of exploratory data analysis. Therefore, corresponding p-values are to be regarded as exploratory ones and no adjustments for multiple testing will be made.

Sample size calculation is performed with a power of 80%.

Statistical hypotheses

The higher 'deterioration in liver function' is indicated by a higher sum of the $N(0,1)$ -standardized changes from baseline to visit 2 in ALT, AST and bilirubin. Therefore, the hypotheses specified before will show – in case of significance – that the potential deterioration in liver function is not relevantly higher upon T than upon S.

Data handling

All data will be listed. Whenever applicable all tables, figures and listings will identify patients using the patient identification (ID) and time of evaluation. For data collected prior to randomization, patients will appear in the listings with the treatment to which they were subsequently allocated.

The actual population presented in a table/figure/listing will be mentioned in the headings.

Tables and listings will be produced in accordance with the principles outlined by the ICH E3 guideline.

Handling missing data and outliers

Every effort will be made to collect all data points in the study. The amount of missing data will be minimized by appropriate management of the randomized, prospective, trial, proper screening of subjects, and training of participating investigators and other authorized staff (e.g. nurses), monitors and study co-coordinator. Since all patients who are randomized will be included in the primary analysis, in those instances where data are missing, missing values will not be imputed.

Prior to database lock a blinded data review meeting will be held to identify remaining data issues, review listings/graphs specifically created for the data review meeting, to assess the impact of protocol violations on the interpretation of data and to trigger last database corrections or an SAP update as applicable.

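### The primary non-inferiority limits assume equal variances although the analysed arms may end up unequal in size; a Welch interval for both limits is a minor, almost cost-free improvement.

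*Combined protocol and SAP*

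**What the plan says.** The Statistical Methods row of the Study Overview gives the primary analysis as "Two sample t-test for mean difference assuming equal variances (testing non-inferiority"). The Statistical methods section under Statistical Analysis and Evaluation says the same: "The non-inferiority will be shown using the two-sample t-tests for mean differences assuming equal variances under the following conditions". The conditions listed there include "number of sides: 1", an alpha of 0.025 and "mean difference : 1.151 (= non-inferiority margin δ").

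Non-inferiority needs two things: an upper confidence limit below 1.151 in the valid-case set (VCAS), which is primary, and confirmation in the FAS. Missing values are not imputed.

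The only variability figure is one overall value from an earlier study, which "provided a standard deviation of 2.3029 for the specified endpoint". No SD is given per arm. On balance, the plan says "Patients will be assigned at a 1:1 ratio to receive either Lipidem or Lipofundin MCT" and sets the size at "160 patients in total (80 per group"). The supplied text names no variance check, unequal-variance alternative or robust standard error.

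**The concern.** A pooled-variance t-test tolerates unequal variances well when the arms are the same size, and poorly when they are not. Randomisation is 1:1, but the arms that enter the test are those left after valid-case exclusions and missing visit 2 values. The section on missing data does say that all randomised patients enter the primary analysis. That conflicts with a valid-case primary analysis, and in any case a patient without visit 2 values has no endpoint when nothing is imputed.

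If the arm with the larger spread loses more patients, the pooled standard error is too small and the upper limit falls below 1.151 too often. In a trial meant to show that liver values do not deteriorate relevantly more on the test emulsion, that error is a false reassurance on safety. One route to this situation is harm that affects only some test-arm patients, who then also leave the valid-case set. This is possible, but the documents do not show that it is likely.

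**Working it through.** **Inputs from the documents.** Margin 1.151, SD 2.3029, one-sided alpha 0.025, power 80%, 160 patients at 1:1.

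**Assumptions, because the documents give no figure.** 128 valid cases in total, their split by arm, the FAS split, and the SD ratio r = SD(test)/SD(reference). Data are normal, the true difference equals the margin, and valid cases are a random subset of the FAS.

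**1. The plan's own figures.** With equal SDs the pooled test holds its level: simulation at the margin gives 0.0248 at 80:80, 0.0251 at 64:64 and 0.0249 at 56:72, so 0.025 reproduces.

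For sample size, the normal approximation is n per arm = 2 × (1.960 + 0.842)² × 2.3029² / 1.151² = 62.8, so 63. The exact noncentral t calculation needs 64 per arm (power 80.1%), or 128 in total. Then 128/(1 − 0.20) = 160, but the 20% loss is an assumption that the documents do not state. It is the reason for using 128 valid cases below.

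**2. Why the pooled standard error goes wrong.** In units of the reference variance:

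- expected pooled variance: [(n_T − 1)r² + (n_S − 1)] / (n_T + n_S − 2), multiplied by (1/n_T + 1/n_S) for the squared standard error
- true squared standard error: r²/n_T + 1/n_S

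At 58:70 (test:reference) with r = 1.5:

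- pooled: (57 × 2.25 + 69)/126 = 1.5655; × (1/58 + 1/70) = 0.04935
- true: 2.25/58 + 1/70 = 0.05308
- ratio of standard errors: √(0.04935/0.05308) = 0.964, so the pooled one is about 3.6% too small

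At 70:58 with r = 1.5:

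- pooled: (69 × 2.25 + 57)/126 = 1.6845; × 0.03153 = 0.05311
- true: 2.25/70 + 1/58 = 0.04938
- ratio: 1.037, so the pooled one is about 3.7% too large

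At 64:64 the two expressions are identical for any r.

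**3. Error of one limit (simulation, nominal 2.5%).**

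| Test:reference | r | Pooled | Welch |
|---|---|---|---|
| 64:64 | 1.5 | 2.5% | 2.5% |
| 58:70 | 1.5 | 2.9% | 2.5% |
| 58:70 | 1.75 | 3.1% | 2.5% |
| 55:73 | 1.5 | 3.2% | 2.5% |
| 55:73 | 1.75 | 3.4% | 2.5% |
| 70:58 | 1.5 | 2.1% | 2.5% |

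**4. Error of the full rule (VCAS and FAS limits both below 1.151, both pooled).**

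| VCAS | FAS | r | Error |
|---|---|---|---|
| 58:70 or 55:73 | 80:80 | 1.5 to 1.75 | about 1.4% to 1.5% |
| 58:70 or 55:73 | 66:74 | 1.5 to 1.75 | about 2.0% to 2.1% |
| 58:70 | 60:72 | 1.5 | about 2.4% to 2.5% |
| 58:70 | 60:72 | 1.75 | about 2.6% |
| 55:73 | 55:73 | 1.5 | about 3.1% to 3.2% |
| 55:73 | 55:73 | 1.75 | about 3.4% |

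**5. Power with equal SDs and no true difference.** Pooled and Welch both give 80.1% at 64:64 and 88.1% at 80:80. At 56:72 they give 79.5% and 79.4%.

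**The case against.** The strongest counter-argument is that the decision does not rest on one limit. A reader might infer from the single-limit figures that the trial's rate of false non-inferiority exceeds 2.5%. The documents do not support that. The FAS must confirm, and with a fairly complete and balanced FAS the error of the full rule is below the nominal level. This stands. It does not remove the point, because the FAS limit is also pooled and unimputed, so a complete FAS is not guaranteed.

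A reader might also infer that the test arm will be both more variable and smaller. The documents give no SD per arm, no dropout rate and no expected valid-case split. In the opposite pattern the pooled limit is conservative. This stands too: the direction of the drift is unknown.

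A larger error appears if the whole 1.151 shift sits in 10% of test patients, which is 11.5 units or about five SDs each. At 58:70 a single pooled limit then has about 4.4% error. In the same setting Welch gives about 3.8%. So about 1.3 of the 1.9 excess points remain under Welch and come mainly from skewness, not from pooling. That figure should not be used to size this point.

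Finally, the pooled test is a common prespecified choice under 1:1 allocation and matches planning from a single SD. The plan also allows an SAP update after the blinded data review. Both are fair, but the supplied text names no unequal-variance option.

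**Conclusion.** The point holds as a conditional and minor weakness. The stated level of each primary limit is secured only if the variances are equal or the analysed arms stay balanced, and the plan ensures neither. Under the assumed splits and SD ratios, a single limit drifts by up to about 0.9 points above nominal (3.4% against 2.5%), or below nominal if the more variable arm is the larger one. The full decision rule exceeds 2.5% only when three things coincide: unequal variances, the more variable arm being the smaller one, and an FAS nearly as depleted and unbalanced as the VCAS. The documents neither establish nor exclude that combination. The case for change is that the remedy costs almost nothing and keeps the interval's level close to nominal in either direction for normal data.

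**What to change.** In the Statistical Methods row of the Study Overview and in the Statistical methods section, replace the equal-variances wording with the Welch (Satterthwaite) two-sample t interval. Apply it to both the VCAS and the FAS limit, and specify it before unblinding; the SAP update that the plan allows before database lock is a suitable place. The margin of 1.151, the one-sided 0.025 and the two-set decision rule stay unchanged. The superiority claim reads the same limits, so it follows without further change.

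The cost is one phrase in two places and a power loss of 0.1 point or less when the variances are in fact equal. The change does not protect against strong skewness.

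### Does leaving the SDs that standardise the liver composite unnamed let concentrated liver harm pass as non-inferior?

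*Combined protocol and SAP*

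**What the plan says.** The Study Overview (Primary Variable) defines the endpoint as the "sum of the N(0,1)-transformed differences in bilirubin, Alanine transaminase (ALT) and Aspartate transaminase (AST) from baseline to visit 2". The Statistical methods section restates it as "defined as the sum of the N(0,1)-transformed differences from baseline in ALT, AST, and bilirubin after 8 weeks of treatment". The Statistical hypotheses section adds the direction: "The higher 'deterioration in liver function' is indicated by a higher sum of the" standardised changes. None of these names the source of the means and SDs: this trial or the previous study, one arm or both, the valid case set or the FAS.

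The previous study is cited only for the SD of the sum, 2.3029, half of which gives the margin of 1.151. No component SDs are given. On the analysis set, Statistical methods states "The primary analysis will be performed for the Valid case set (FAS for sensitivity" purposes), and requires the FAS to confirm the result. The section headed "Handling missing data and outliers" reads differently, "Since all patients who are randomized will be included in the primary analysis", and gives no rule for outliers beyond a blinded data review.

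**The concern.** The means cancel in a difference between arms, but the SDs do not. The natural reading of an N(0,1) transformation is a z-score with this trial's own SD over all patients. A very large rise in a few test-arm patients then raises both the numerator and the divisor, so past some point more severe harm no longer gives a larger standardised difference. That sits badly with the statement that a higher sum indicates more deterioration.

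This is the only confirmatory test in a trial whose primary objective is safety. Eligibility does not rule out large rises on treatment. It excludes "Persistent high total bilirubin values in medical history of last 6 months", intrahepatic cholestasis, severe hepatic insufficiency, hepatitis B or C and alcohol abuse, but sets no ALT or AST limit. If the valid case set and the FAS were each restandardised, they could also use different divisors.

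**Working it through.** **The plan's own figures.** 2.3029/2 = 1.15145, which is the stated margin. With one-sided alpha 0.025 and a true difference of zero, the exact t calculation gives 64 per arm for 80.1% power. With all 80 per arm evaluable, power is 88.1%.

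**Correlation implied by the SD.** If the three components had unit SD in the previous study, the variance of the sum is 3 + 6r, so r = (2.3029² − 3)/6 = (5.3033 − 3)/6 = 0.384. This mean pairwise correlation is used below.

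**Ceiling.** Let k of 80 test patients rise by M background SDs in one marker, no reference patient rise, and p = k/160. The raw contrast is 2pM and the both-arm variance is 1 + M²p(1 − p). The standardised contrast is 2pM/√(1 + M²p(1 − p)), which tends to 2√(p/(1 − p)) as M grows.

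- k = 4: 2√(0.025/0.975) = 0.32. At M = 10 the contrast is 0.50/√3.4375 = 0.27; at M = 100 it is 5.00/√244.75 = 0.32.
- k = 8: 2√(0.05/0.95) = 0.46.

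**Chance of concluding non-inferiority.** The planned rule (upper 95% t limit below 1.151) was simulated with 80 per arm and trivariate normal background changes. The sizes and frequencies of the rises are assumptions. Where three figures are given, they are for rises of 5 / 10 / 20 SD.

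| Scenario | Both-arm SDs | Reference-arm SDs |
|---|---|---|
| No harm | 88% | 88% |
| Bilirubin, 10% test vs 0% | 66 / 62 / 62% | 36 / 6 / 0.3% |
| ALT and AST, 5% test vs 0% | 53 / 38 / 28% | 32 / 8 / 2% |
| Uniform shift of 0.384 SD in all three (the margin) | 2.5% | 2.5% |
| One test patient, ALT and AST, 10 / 20 SD | 76 / 73% | 52 / 6% |
| One reference patient, ALT and AST, 10 / 20 SD, plus the margin shift in the test arm | 13 / 35% | 22 / 59% |
| Bilirubin, 2% in each arm, no treatment effect | 90 / 91 / 93% | 88 / 86 / 83% |
| ALT and AST, 2% in each arm, no treatment effect | 88 / 88 / 87% | 84 / 79 / 72% |

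In the row with one reference patient, that patient also lowers the true contrast, so only the two columns should be compared.

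**Where masking stops.** If 4 of 80 test patients rise in all three markers, both-arm SDs give 20 / 0.4 / 0%, because the SD of the sum grows as well. With bilirubin alone at 20 SD and both-arm SDs, the pass rate is about 60% at 8 of 80, 49% at 11, 34% at 16 and 6% at 32. The odds are thus about even at 11 of 80, far below the roughly 40 of 80 at which the point estimate's ceiling reaches 1.151, because the rule uses the upper confidence limit.

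**Two analysis sets.** One patient with a 10 or 20 SD rise counted in only one set multiplies that component's SD by √(1 + (M²/160)(159/160)), which is 1.27 or 1.87. Both sets must pass, so a divergence would show.

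**The case for a change.** The strongest case for a change is that the omission is real and the ceiling is algebra. As written, the primary endpoint cannot be programmed without a choice that may alter the verdict. In the isolated bilirubin scenario, going from 5 to 20 SD hardly moves the pass rate. Pooling the SDs within arms masks almost as much. The component breakdown comes only after non-inferiority and cannot reverse it, and no DSMB is appointed. Naming reference-arm SDs would take one sentence and, without outliers, cost about 0.6 points of power (87.7 against 88.3% at 80 per arm).

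The omission and the arithmetic stand. The case for a different divisor does not. The table shows reference-arm SDs failing in the opposite way: one ill patient in the test arm can decide the trial, one in the reference arm hides diffuse harm better than both-arm SDs would, and equal incidence in the two arms costs up to 15 points of power (72 against 87%). They also protect only partly once the reference arm has cases: for bilirubin in 10% against 2%, the pass rate at 10 / 20 SD is 40 / 34%, against 74 / 74% with both-arm SDs. Supportive analyses with other SDs, or raw-unit intervals, would be harmless. They would largely repeat the planned component breakdown, the liver markers and adverse events among the secondary variables, and the full data listings, and would leave the non-inferiority conclusion as it is.

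**Conclusion.** No change to the plan is called for. The SD source is a missing detail, not a demonstrated error. No section says that both arms are pooled. If they are, the 2.5% level holds and 1.151 remains a valid effect-size margin. One set of SDs used in both analysis sets is the sensible way to fill the gap, and the Handling missing data and outliers section already allows an SAP update at the blinded review before database lock. The differing statements on the primary analysis set are a separate wording matter.

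Masking is marked for one marker in a minority of the test arm (about 62% passing at 10% incidence and 20 SD), weaker when ALT and AST rise together (28% at 5% incidence and 20 SD), nearly absent when all three rise by 10 SD or more, and negligible for a uniform shift at the margin. These figures rest on assumed rises of 5 to 20 SD, no cases in the reference arm, normal background changes and a common correlation of 0.384. The choice between divisors is a fair trade-off, with no option better throughout.
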